1 **Immediate Skin-to-Skin Contact and Breastfeeding During Caesarean Section: A**
2 **Randomized Controlled Trial on Early Neonatal Hypoglycemia in Late Preterm**
3 **and Term Infants**

4 **1. Introduction**

5 Neonatal hypoglycemia is a common and serious metabolic issue in late preterm
6 and term infants, potentially leading to severe neurodevelopmental sequelae if not
7 promptly managed¹. The World Health Organization strongly endorses skin-to-skin
8 contact (SSC), recommending that the practice should begin immediately after birth by
9 placing the naked infant on the mother's bare chest. This approach is vital for stabilizing
10 glucose levels and supporting neonatal adaptation to extrauterine life².

11 Despite the well-documented advantages of SSC in vaginal births, such as thermal
12 regulation, breastfeeding initiation, and bonding, implementing this practice during
13 cesarean sections (CS) presents significant challenges³. These challenges primarily
14 stem from the need to maintain a sterile surgical environment and the logistical
15 complexities of performing SSC immediately post-surgery⁴. However, research
16 indicates that immediate, continuous SSC within 5–10 minutes of neonatal delivery
17 during and after CS can foster earlier breastfeeding initiation, increase breastfeeding
18 self-efficacy and exclusive breastfeeding rates during hospitalization, and enhance
19 maternal satisfaction⁵. Additionally, it can reduce the incidence of neonatal
20 hypothermia and cumulative blood loss within 24 hours postpartum.

21 Despite the advantages noted in the literature, there is limited systematic research
22 on the implementation of SSC during CS and its specific impact on neonatal
23 hypoglycemia and breastfeeding outcomes⁴. This study aimed to address this gap by
24 evaluating the effects of immediate SSC and breastfeeding during CS on early neonatal
25 hypoglycemia in late preterm and term infants. Through a randomized controlled trial,
26 we sought to provide robust evidence on the feasibility and benefits of integrating these
27 practices into standard CS protocols. Our findings could inform clinical guidelines,
28 enhance care practices for cesarean deliveries, and ultimately improve neonatal health
29 outcomes and breastfeeding success.

1
2
3
4
5
6
7
8
9
10
11
12
13
14
15
16
17
18
19
20
21
22
23
24
25
26
27
28

2. Material and Methods

2.1 Study Design

This study will adopt a pragmatic, parallel-design, two-arm randomized controlled exploratory framework. The article’s reporting will adhere to the Consolidated Standards of Reporting Trials (CONSORT) guidelines⁶.

2.2 Study Setting, Recruitment and Ethics

This study will be conducted at Qingdao Municipal Hospital in China between July 2022 and June 2024. The hospital is accredited as baby-friendly and adheres to the Ten Steps to Successful Breastfeeding as outlined by the Baby-Friendly Hospital Initiative (BFHI) by UNICEF and WHO⁷. A total of 344 eligible mother-neonate pairs will be recruited and allocated into the experimental group (EG) and control group (CG) at a 1:1 ratio. Written informed consent will be obtained from each participant.

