4 **2.10 Sample Size**

5 The sample size was determined based on a preliminary trial with 258
6 participants⁵. In this trial, the Early Essential Newborn Care (EENC) group exhibited
7 a lower incidence of neonatal hypoglycemia compared to the control group receiving
8 conventional care (0 vs. 5.3%, $P=0.007$). Using G*Power software version 3.1.7, with
9 a two-sided type I error (α) of 0.05, a power ($1 - \beta$) of 90%, test family set to 'exact,'
10 and the statistical test 'proportions: inequality, two independent groups,' it was
11 calculated that at least 148 patients were required in each group. To account for an
12 anticipated 20% dropout rate, the total sample size was adjusted to 356 participants,
13 with 178 allocated to each group.

14 **2.11 Statistical Analysis**

15 The data analysis will be performed using SPSS 21.0 (SPSS Inc., Chicago, IL).
16 Quantitative variables will be expressed as mean \pm standard deviation. The T-test will
17 be employed for normally distributed data, while the Mann-Whitney U test will be
18 used for non-normally distributed data. Categorical variables will be summarized as
19 frequencies and percentages and analyzed with the Chi-squared test. All statistical
20 tests are two-sided, and a P-value of less than 0.05 is considered significant.

21 **2.12 Ethics**

22 This study will adhere to the ethical standards set by the relevant institutional and
23 national review committees. Approval was granted by the Institutional Research
24 Human or Animal Ethics Committee of Qingdao Municipal Hospital (2023 Lin Shen
25 Zi No. 122), and all procedures complied with the revised 2013 Declaration of
26 Helsinki.

IMMEDIATE SKIN-TO-SKIN CONTACT DURING CAESAREAN SECTION

References

- 1
- 2 1. Roeper M, Hoermann H, Kummer S, Meissner T. Neonatal hypoglycemia: lack of
3 evidence for a safe management. *Front Endocrinol (Lausanne)*. 2023;14:1179102.
- 4 2. World Health Organization W. Skin-to-skin contact helps newborns breastfeed.
5 [https://www.who.int/westernpacific/news-room/feature-stories/item/skin-to-skin-
7 contact-helps-newborns-breastfeed](https://www.who.int/westernpacific/news-room/feature-stories/item/skin-to-skin-
6 contact-helps-newborns-breastfeed). Accessed July 23, 2024.
- 8 3. Immediate and Sustained Skin-to-Skin Contact for Healthy Late Preterm and Term
9 Newborns After Birth: AWHONN Practice Brief Number 14. *Journal of Obstetric,
10 Gynecologic & Neonatal Nursing*. 2021;50(6):e13-e15.

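### The protocol gives two recruitment totals, 344 and 356, and neither leaves the required 148 per group after the anticipated 20% dropout

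*Protocol*

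**What the plan says.** Protocol section 2.2 (Study Setting, Recruitment and Ethics) fixes recruitment: "A total of 344 eligible mother-neonate pairs will be recruited and allocated into the experimental group (EG) and control group (CG"), in a 1:1 ratio. That is 172 pairs per group.

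Protocol section 2.10 (Sample Size) starts from hypoglycemia incidences of 0 and 5.3%, "a two-sided type I error (α) of 0.05", 90% power and a test from the exact family. It reports that it was "calculated that at least 148 patients were required in each group". It then allows for loss: with an "anticipated 20% dropout rate, the total sample size was adjusted to 356 participants", "with 178 allocated to each group".

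Protocol section 2.11 (Statistical Analysis) says that categorical variables, which include the primary outcome, are summarized as "frequencies and percentages and analyzed with the Chi-squared test".

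**The concern.** There are two separate defects.

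1. **Two totals.** Sections 2.2 and 2.10 both describe pairs allocated to the two groups, so one figure cannot be read as enrolled and the other as analysed. They differ by 12 pairs, and the protocol does not say which governs. A trial that stopped at 344 would have met its target under section 2.2 and fallen 12 pairs short under section 2.10.

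2. **The dropout allowance.** Section 2.10 presents 356 as the number that protects 148 per group against 20% dropout. It does not do so, because the 20% was added to 148 when it should have been taken off the enrolled number.

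At stake is whether a reader can tell if recruitment was completed, and how much loss the design can absorb before it falls below its own minimum.

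**Working it through.** **Inputs**
- Required per group: 148 (section 2.10)
- Anticipated dropout: 20% (section 2.10)
- Totals: 356, or 178 per group (section 2.10); 344, or 172 per group (section 2.2)
- Event rates 0 and 5.3%, two-sided α 0.05 (section 2.10)

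**Step 1: reproduce 356.** 148 × (1 + 0.20) = 177.6, rounded up to 178; 178 × 2 = 356. This matches the protocol exactly.

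**Step 2: the allowance that retains 148.** n/(1 − d) = 148/0.80 = 185 per group, 370 in total. The enrolled number is short of this by 185 − 178 = 7 per group at 356 and by 185 − 172 = 13 per group at 344.

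**Step 3: try to derive 344.** 172/148 = 1.162. Multiplying by 1.2 gives 356 and dividing by 0.8 gives 370, so neither rule yields 344. The block size of four (section 2.5) does not explain it, since 344/4 = 86 and 356/4 = 89 are both whole numbers.

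**Step 4: what a 20% loss leaves, and what loss is tolerated.**

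| Total | Per group | After 20% loss | Shortfall against 148 | Loss that still leaves 148 |
|---|---|---|---|---|
| 356 | 178 | 178 × 0.8 = 142.4 | about 6 | 1 − 148/178 = 16.9% |
| 344 | 172 | 172 × 0.8 = 137.6 | 10 to 11 | 1 − 148/172 = 14.0% |

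**Step 5: power.** With a true rate of 0 in one group, that group has no events, so power is the probability that a Binomial(n, 0.053) count in the other group reaches the smallest count that rejects. For n from 137 to 148:
- Uncorrected chi-square rejects at 4 or more events. For x against 0, z = √x / √(1 − x/(2n)). At n = 142 this is 2.01 for x = 4 and 1.74 for x = 3, against 1.96.
- Two-sided Fisher rejects at 6 or more. At n = 142, p = 0.060 for 5 against 0 and 0.030 for 6 against 0.

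| Per group | Uncorrected chi-square | Fisher exact |
|---|---|---|
| 148 | 95.7% | 80.2% |
| 142 (from 356) | 94.6% | 76.9% |
| 138 / 137 (from 344) | 93.8% / 93.6% | 74.5% / 73.9% |

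The loss relative to 148 is:
- **At 356:** 95.7 − 94.6 = 1.1 points (chi-square) or 80.2 − 76.9 = 3.3 points (Fisher).
- **At 344:** 1.9 to 2.1 points (chi-square) or 5.7 to 6.3 points (Fisher).

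The tests diverge because the expected events per group under the null are few: n × 0.053/2 = 3.6 at 137 and 3.9 at 148.

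**The case against.** Nobody can argue away the conflict between 344 and 356. The other side's case concerns weight.

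- **Multiplying by 1.2 is a common shortcut, and the cost is small.** About 6 participants per group are at issue at 356. With an uncorrected chi-square test, power stays above 90% in every scenario. This stands as far as consequence goes. The larger losses come from Fisher's test, which section 2.11 does not name. However, section 2.10 specifies an exact test, and a continuity-corrected chi-square has the same rejection threshold as Fisher here (p = 0.071 at 5 events and 0.039 at 6, with n = 142). The size of the loss therefore depends on a choice the protocol leaves open.
- **The 20% belongs to section 2.10 and is not attached to 344.** This is fair. The figures of 137 to 138 hold only if the same dropout rate is applied to the section 2.2 total. Likewise 356 is the only total with a stated derivation; what is unknown is where 344 comes from and which figure governs recruitment.
- **Loss may be well under 20%.** The primary outcome is measured in hospital at 1, 3 and 6 hours after birth, and 356 tolerates 16.9%. This also stands. But some eligibility conditions, such as the Apgar scores and bleeding during surgery, are known only at or after delivery, so appreciable loss after enrolment cannot be ruled out. In any case 20% is the protocol's own planning figure, and if it is too high the text should say so.
- **The trial calls itself exploratory.** It nevertheless gives a powered calculation, and it needs one planned size against which recruitment can be reported.

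**Conclusion.** The concern holds. The contradiction between sections 2.2 and 2.10 is plain on the page and is the weightier defect: a core design quantity has two values, 12 pairs apart. The dropout error is smaller but equally clear, since section 2.10 does not meet its own minimum under its own assumption.

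The power figures assume that the true rates are 0 and 5.3% and that the full 20% is lost equally from both groups. The conclusion takes 148 as given. Whether 148 delivers the stated 90% is a different question and no part of this point; for that reason the differences in power matter here and the absolute levels do not.

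This should be corrected before the sample size is relied on, even though the power cost is modest.

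**What to change.** State one total in both section 2.2 and section 2.10, and show how it was obtained. Then make the dropout sentence agree with it in one of two ways:

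- **Restate the tolerated loss.** For example, with 178 per group, dropout of up to 16.9% leaves 148 per group; with 172 per group, up to 14.0%.
- **Keep 20% and restate what remains.** That is about 142 per group from 356, or 137 to 138 from 344, with the power for that number under a named test that matches section 2.11.

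Either is a change of wording only. For reference, the total consistent with 148 per group and 20% loss is 370 (185 per group), which is 14 pairs more than 356 and 26 more than 344. Enrolling more is not needed to resolve this point.

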2.3 Inclusion Criteria

Inclusion criteria are as follows: (a) mothers aged 18 years or older with a singleton pregnancy, gestational age between 34+1 and 41+6 weeks; (b) undergoing elective cesarean section with epidural, subarachnoid block, or combined spinal-epidural anesthesia, willing to engage in mother-infant SSC during and after the surgery, without experiencing severe reactions to anesthesia like vomiting or shivering that could affect SSC; (c) having intention to breastfeed with no major contraindications (e.g., hepatitis B, syphilis, HIV, or other infectious diseases); (d) newborns with Apgar scores above 8 at 1 and 5 minutes, a strong sucking reflex, and no critical neonatal conditions requiring transfer.

2.4 Exclusion criteria

Exclusion criteria are as follows: (a) serious pregnancy complications such as placenta previa, placenta accreta spectrum, eclampsia, and grade 3 or higher cardiac issues per NYHA standards; (b) challenges in initiating mother-infant SSC include emergencies such as neonatal asphyxia or respiratory distress, maternal excessive bleeding during surgery, and maternal infectious dermatoses; (c) previous breast

IMMEDIATE SKIN-TO-SKIN CONTACT DURING CAESAREAN SECTION

1 surgeries such as biopsies or augmentations, nipple inversions complicating
2 breastfeeding, or taking medications affecting lactation.

3 **2.5 Randomization and Blinding**

4 A randomization sequence will be generated using Microsoft Excel 2010 with
5 block randomization in blocks of four via a central system. Random distribution cards
6 will be placed in numbered opaque envelopes, each corresponding to a card. As
7 eligible participants enrolled, envelopes will be opened sequentially to assign
8 treatments based on predetermined groupings. The randomization plan will be
9 designed by a public health graduate student specializing in medical statistics, who
10 will not be involved in the clinical phase. Staff performing SSC during and after
11 cesarean will be blinded to the randomization procedure, and data collectors and
12 statistical analysts will be unaware of patient groupings. However, blinding of patients
13 will not be feasible.

14 **2.6 Experimental Group (EG)**

15 2.6.1 Administration of SSC and BF during CS

16 A multidisciplinary team, including obstetricians, pediatricians, anesthetists,
17 nursing staff, and other personnel, collaborates to implement a SSC and BF during CS
18 (skin-to-skin contact and breastfeeding during cesarean section) protocol for the
19 intervention. Following spinal anesthesia, the gynecologist initiates surgery with double
20 sterile gloves and arm sleeves. The pediatrician remains on standby in the adjacent
21 neonatal resuscitation room to manage any distress in the newborn. As the neonate is
22 delivered, the surgical drape is lowered, allowing the parents to witness the birth. The
23 neonate, facing the parents, is gently placed on the mother's chest by an obstetric nurse.
24 Before resuming the procedure, the surgeon removes one pair of gloves and sleeves,
25 and the sterile barrier is reestablished. If the neonate exhibits no signs of distress, it
26 remains in SSC with the mother for as long as possible, ideally throughout the cesarean.
27 The obstetric nurse monitors the neonate during SSC and assists the mother in holding
28 the newborn. In cases of maternal or neonatal discomfort, the neonate may be handed

IMMEDIATE SKIN-TO-SKIN CONTACT DURING CAESAREAN SECTION

1 to an obstetric nurse or pediatrician. All neonates are examined by the pediatrician
2 within an hour post-delivery in the recovery ward.

3 2.6.2 Immediate SSC and early breastfeeding initiation

4 Upon birth, the neonate is promptly placed prone on the mother's chest, with their
5 head turned to one side for optimal skin contact. The drying process begins within 5
6 seconds and is completed within 20 to 30 seconds while the neonate remains on the
7 mother's chest. Delayed cord clamping is practiced, with the cord clamped
8 approximately 1-3 minutes after birth. Breastfeeding cues such as tongue movements
9 or head turning are monitored, and the obstetric nurse assists the mother in initiating
10 breastfeeding as soon as possible. SSC continues throughout the cesarean procedure,
11 and upon completion, the newborn is temporarily separated from the mother for safety
12 during transfer to the surgical cart. SSC is resumed immediately post-transfer and
13 continues for a cumulative duration of at least 90 minutes. The neonate's skin color,
14 breathing, and feeding responses are continuously observed.

15 2.6.3 Routine newborn care

16 Newborn eye care, vitamin K1 administration, immunizations, weighing, and
17 standard examinations are conducted before the neonate is transferred to the ward.

18 **2.7 Control Group (CG)**

19 2.7.1 Delayed SSC and breastfeeding

20 The neonate is dried within 20-30 seconds after birth, the cord is clamped after 1-
21 3 minutes, and then the neonate is sent to the ward to wait for the mother to complete
22 the surgery. Immediate SSC is initiated within one hour after birth and maintained with
23 the mother for at least 90 minutes post-surgery, during which the neonate's skin color
24 and breathing are continuously monitored. The obstetric nurse supports the mother in
25 initiating breastfeeding at the earliest opportunity.

26 2.7.2 Routine newborn care

27 Newborn eye care, vitamin K1 administration, immunizations, weighing, and
28 standard examinations are conducted before the neonate is transferred to the ward.

29 **2.8 Outcome Indicators**

IMMEDIATE SKIN-TO-SKIN CONTACT DURING CAESAREAN SECTION

1 2.8.1 Primary outcome

2 (A) Incidence of neonatal hypoglycemia: Neonatal blood glucose levels will be
3 assessed using the Stat Strip Xpress glucose meter at 1, 3, and 6 hours after birth.
4 Hypoglycemia is categorized as follows: mild hypoglycemia (overall) at <45 mg/dL,
5 moderate-to-severe at <36 mg/dL, and severe at <18 mg/dL. Treatment will be
6 initiated if levels dropped below 25 mg/dL or if symptoms like shakiness, tachycardia,
7 pallor, hypothermia, hunger, sweating, or weakness appeared⁸. In such cases, 10
8 ml/kg of formula will be administered, followed by a recheck after 0.5 hour. If levels
9 rise above 40 mg/dL, subsequent checks occurs every 3 hours⁹. Persistent levels
10 below 50 mg/dL necessitates continued formula feeding and monitoring, or
11 transferred to neonatal care if needed.

12 2.8.2 Secondary outcome

13 (A) Breastfeeding initiation and duration of first breastfeeding, characterized by
14 newborns correctly latching onto the nipple and areola, and establishing regular,
15 effective sucking and swallowing, will be immediately assessed post-operation, with
16 timing recorded to the minute.

17 (B) Onset of lactogenesis II, approximately 72 hours post-delivery, marked by
18 significant milk secretion perceived by the mother as breast fullness, confirmed by
19 observing and squeezing the areola to assess milk spillage, will be assessed from
20 delivery to pre-discharge, with timing recorded to the hour postpartum.

21 (C) Exclusive breastfeeding rate during hospitalization, where newborns are
22 exclusively breastfed except for vitamins and minerals. This rate will be calculated for
23 mothers who underwent cesarean delivery in both study groups.

24 **2.9 Data Collection and Management**

25 Researchers will contact all women scheduled for cesarean deliveries within 24
26 hours before the procedure. Led by the principal investigator and an experienced
27 research assistant, the team will conduct face-to-face interviews to gather
28 demographic and obstetric information. Details regarding the duration of SSC, the
29 initiation and duration of the first breastfeeding session, exclusive breastfeeding

IMMEDIATE SKIN-TO-SKIN CONTACT DURING CAESAREAN SECTION

1 during hospitalization, as well as the infant's safety and blood glucose levels, will be
2 continuously collected and recorded by trained staff during and after elective cesarean
3 sections. All data will be anonymized and de-identified for further evaluation.

4 **2.10 Sample Size**

5 The sample size was determined based on a preliminary trial with 258
6 participants⁵. In this trial, the Early Essential Newborn Care (EENC) group exhibited
7 a lower incidence of neonatal hypoglycemia compared to the control group receiving
8 conventional care (0 vs. 5.3%, $P=0.007$). Using G*Power software version 3.1.7, with
9 a two-sided type I error (α) of 0.05, a power ($1 - \beta$) of 90%, test family set to 'exact,'
10 and the statistical test 'proportions: inequality, two independent groups,' it was
11 calculated that at least 148 patients were required in each group. To account for an
12 anticipated 20% dropout rate, the total sample size was adjusted to 356 participants,
13 with 178 allocated to each group.

14 **2.11 Statistical Analysis**

15 The data analysis will be performed using SPSS 21.0 (SPSS Inc., Chicago, IL).
16 Quantitative variables will be expressed as mean \pm standard deviation. The T-test will
17 be employed for normally distributed data, while the Mann-Whitney U test will be
18 used for non-normally distributed data. Categorical variables will be summarized as
19 frequencies and percentages and analyzed with the Chi-squared test. All statistical
20 tests are two-sided, and a P-value of less than 0.05 is considered significant.

21 **2.12 Ethics**

22 This study will adhere to the ethical standards set by the relevant institutional and
23 national review committees. Approval was granted by the Institutional Research
24 Human or Animal Ethics Committee of Qingdao Municipal Hospital (2023 Lin Shen
25 Zi No. 122), and all procedures complied with the revised 2013 Declaration of
26 Helsinki.

IMMEDIATE SKIN-TO-SKIN CONTACT DURING CAESAREAN SECTION

References

- 1
- 2 1. Roeper M, Hoermann H, Kummer S, Meissner T. Neonatal hypoglycemia: lack of
3 evidence for a safe management. *Front Endocrinol (Lausanne)*. 2023;14:1179102.
- 4 2. World Health Organization W. Skin-to-skin contact helps newborns breastfeed.
5 [https://www.who.int/westernpacific/news-room/feature-stories/item/skin-to-skin-
7 contact-helps-newborns-breastfeed](https://www.who.int/westernpacific/news-room/feature-stories/item/skin-to-skin-
6 contact-helps-newborns-breastfeed). Accessed July 23, 2024.
- 8 3. Immediate and Sustained Skin-to-Skin Contact for Healthy Late Preterm and Term
9 Newborns After Birth: AWHONN Practice Brief Number 14. *Journal of Obstetric,
10 Gynecologic & Neonatal Nursing*. 2021;50(6):e13-e15.

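### A constant, disclosed block size of four lets anyone in enrolment who knows it and tracks earlier assignments predict one third of allocations with certainty.

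*Protocol*

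**What the plan says.** Section 2.5 of the protocol (Randomization and Blinding) sets one block size and prints it: "block randomization in blocks of four via a central system". Allocation is then by cards in numbered opaque envelopes: "eligible participants enrolled, envelopes will be opened sequentially to assign" the treatments. Section 2.2 gives the ratio, "allocated into the experimental group (EG) and control group (CG) at a 1:1 ratio", and the setting: "This study will be conducted at Qingdao Municipal Hospital in China". No stratification is mentioned, so there is one running sequence of blocks.

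On masking, section 2.5 makes three statements:

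- Patients are not masked ("However, blinding of patients" is said not to be feasible).
- The staff who give skin-to-skin contact (SSC) are kept unaware of the randomization procedure. The statement does not say they are unaware of the arm.
- Data collectors and analysts do not know the groupings.

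The person who designs the list takes no part in the clinical phase. The section does not say who enrols, who opens the envelopes, or whether those people know the block size or the earlier assignments.

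Sections 2.6 and 2.7 describe arms that look different in theatre. In the experimental group the neonate lies on the mother's chest during surgery; in the control group it is taken to the ward while surgery is completed.

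**The concern.** Opaque envelopes hide the card, but not an assignment that can be deduced from those before it. With a constant block of two and two, the fourth assignment always follows from the first three, and the third follows whenever the first two match. Each delivered arm is visible to the theatre team, there is one sequence at one site, and the block size is in the protocol. The information needed for the deduction could therefore reach someone who decides on enrolment.

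Foreknowledge matters because some entry criteria in section 2.3 need judgement before birth: willingness to engage in SSC and, possibly, whether a reaction to anesthesia is severe enough to interfere with it. Eligible gestation runs from 34+1 to 41+6 weeks, so pairs may differ in their risk of hypoglycemia. If someone who expected a given arm enrolled or passed over pairs accordingly, the groups would no longer be comparable, and no later analysis could fully repair that. The planned primary outcome may also be rare, in which case a handful of pairs could decide the result.

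**Working it through.** **Inputs.** Block size 4 (section 2.5); ratio 1:1, so two E and two C per block (section 2.2); one site and no stated strata. Total: "A total of 344 eligible mother-neonate pairs will be recruited" in section 2.2, but 356 in section 2.10 ("anticipated 20% dropout rate, the total sample size was adjusted to 356 participants"). The two totals differ, which is a separate matter; the share below is the same for either. The protocol gives no predictability figure to reproduce.

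**Step 1: certain allocations.** An allocation is certain when one arm's two places in the block are already used. The guess rule is to name the arm with more places left, scoring one half at ties. All six blocks are equally likely.

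| Block | Certain positions | Expected correct guesses |
|---|---|---|
| EECC | 3rd, 4th | 0.5 + 0 + 1 + 1 = 2.5 |
| CCEE | 3rd, 4th | 2.5 |
| ECEC | 4th | 0.5 + 1 + 0.5 + 1 = 3 |
| ECCE | 4th | 3 |
| CECE | 4th | 3 |
| CEEC | 4th | 3 |

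Certain: (2 × 2 + 4 × 1) / 24 = 8/24 = 33.3%. By position: 0%, 0%, 33.3%, 100%.

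In numbers:

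- 344 / 4 = 86 blocks, giving 86 fourth places plus on average 86/3 = 28.7 third places, or about 115.
- 356 / 4 = 89 blocks, giving 89 + 29.7, or about 119.

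One third is a long-run average. In a single list the share must lie between 25% (no EECC or CCEE block) and 50% (only such blocks).

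**Step 2: best guess.** (2 × 2.5 + 4 × 3) / 24 = 17/24 = 70.8%, against 50% by chance. A simulation of 344 allocations repeated 300 times gave 33.4% certain and 70.8% correct.

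**Step 3: other block schemes.** For the varying schemes the observer is assumed to know the possible sizes and all past assignments, but not the size of the current block (simulated).

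| Scheme | Certain | Best guess correct |
|---|---|---|
| Fixed 4 | 33.3% | 70.8% |
| Fixed 6 | 25% | 68.3% |
| Fixed 8 | 20% | 66.6% |
| Random 4/6 | about 5% | about 69% |
| Random 4/6/8 | about 2% | about 68% |

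**Step 4: how few pairs could matter.** The protocol states no expected event count. Section 2.10 plans on 0 versus 5.3% from a cited trial. If that control rate applied here, the expected control events would be 0.053 × 148 = 7.8, 0.053 × 172 = 9.1 or 0.053 × 178 = 9.4, with none in the experimental group. At 148 per group:

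| Events, E vs C | Chi-squared P (no continuity correction) | Fisher P |
|---|---|---|
| 0 vs 8 | 0.004 | 0.007 |
| 1 vs 7 | 0.03 | 0.067 |
| 2 vs 6 | 0.15 | 0.28 |

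A shift of one or two events between arms would move the result across the 0.05 line, depending on the test.

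**The case against.** The strongest reply is that the document shows no such observer. The envelopes are opaque and numbered, the list designer stays out of the clinic, and SSC staff are said to be unaware of the randomization procedure. That can be read as withholding the block size from the very people who see the arms. Section 2.9 places recruitment interviews within 24 hours before surgery and does not say that recruiters attend theatre. This has force: the one-third figure is conditional, and a reader should not infer that staff could in fact foresee a third of the assignments. The statement does not close the gap, however. It does not cover those who enrol or open envelopes, it cannot hide a delivered arm, and a constant block of four can be worked out from a visible sequence.

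Three further limits stand.

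- A reader might add the sucking-reflex criterion to the routes for selective enrolment. It does not fit. In the experimental group the arm must be known before birth, and the reflex can be judged only afterwards. Dropping a pair on it would be exclusion with the arm already known, which block size does not affect.
- The event count rests on a rate from a cited trial. The protocol does not show whether that trial defined hypoglycemia as section 2.8.1 does.
- Varying the block size removes nearly all certainty but little of the advantage in guessing.

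**Conclusion.** The point holds as a weakness in a stated rule that is cheap to improve. For someone involved in enrolment who knows or infers the block size and the earlier assignments in the block, one third of allocations are certain and 71% can be guessed. The arithmetic is exact; whether such a person exists cannot be told from the protocol.

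Two stronger readings are not supported. One is that prediction or selective enrolment took place, so that the comparison is biased: nothing in the protocol shows this. The other is that the trial is open throughout: it is open to patients and to theatre staff, while data collectors and analysts are stated to be masked. The statement that a few pairs could change the result depends on the assumed 5.3% control rate, that is, on about 8 to 9 events in total.

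**What to change.** For every envelope not yet opened, generate a new list with randomly varying block sizes, for example 4, 6 and 8. Delete the block size from the clinical protocol and record it only in a document held by the independent statistician. Section 2.5 could say: *Allocation uses permuted blocks of randomly varying size; the sizes are not available to anyone who recruits, enrols, opens envelopes or gives care.* The same section should name the roles that enrol and that open the envelopes.

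The cost is a new list and one or two sentences, with no effect on sample size or analysis. Stopping in mid-block could leave a slightly larger imbalance: at most 4 pairs with a block of 8, against 2 with a block of 4. The gain is mainly the removal of certainty (33% to about 2%); best-guess accuracy drops only from 71% to about 68%.

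Section 2.2 gives a study period ending in June 2024, and the reference list has web pages accessed in July 2024, so there may be no envelopes left. In that case the list cannot be changed. The report should then state the fixed block size, who enrolled, who opened envelopes and who knew the size, and name this as a limitation on allocation concealment.
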